9.6 Safety Oversight

DATA AND SAFETY MONITORING PLAN

The proposed research does not include any IND or Investigational Device Exemption (IDE). All study procedures will be approved by IRBs at each institution, and the site will notify IRBs, according to their guidelines, of any AEs that could possibly be attributed to participation in the study.

A DSMB will be created to review this study. The DSMB will be approved by the DMID. Meetings of the DSMB will be arranged, facilitated, and documented by CROMS SOCS. The initial responsibility of the DSMB will be to approve the initiation of this clinical trial. After this approval and annually during the course of the trial, the DSMB responsibilities are to:

- Review the research protocol, IC documents, and plans for data and safety monitoring;
- Evaluate the progress of the trial, including periodic assessments of data quality and timeliness, subject recruitment, accrual and retention, subject risk versus benefit;
- Performance of the trial site, and other factors that can affect study outcome;
- Consider factors external to the study when relevant information becomes available, such as scientific or therapeutic developments that may have an impact on the safety of the subjects or the ethics of the trial;
- Review clinical centers performance, make recommendations and assist in the resolution of problems reported by the PI;

- Protect the safety of the study subjects;
- Report on the safety and progress of the trial;
- Review SAEs for increased frequency, although SAEs are not anticipated for this trial;
- Make recommendations to the sponsor, the PI, and if required, to the FDA concerning continuation, termination or other modifications of the trial based on the observed beneficial or adverse effects of the treatment under study;
- Ensure the confidentiality of the trial data and the results of monitoring;
- Assist the PI by commenting on any problems with study conduct, enrollment, and sample size and/or data collection.

Members will likely include experts in STDs, clinical trials methodology, and biostatistics. Members will consist of persons independent of the investigators who have no financial, scientific, or other conflict of interest with the trial. Written documentation attesting to absence of conflict of interest will be required.

The first meeting, also known as the organizational meeting, will take place before initiation of the study to discuss the protocol, approve the commencement of the study, and to establish the charter to monitor the study. The DSMB will meet annually. A final DSMB meeting will take place at the close-out of the study. An ad hoc emergency meeting of the DSMB can be called at any time by any party should question of subject safety arise. The PI and the SI and/or other study team members will be present (via conference call) at each meeting. A simple majority will be considered a quorum for DSMB meeting and voting purposes. The DSMB will advise DMID of its findings.

10 CLINICAL MONITORING

10.1 Site Monitoring Plan

DMID, the sponsoring agency, or its designee will conduct site-monitoring visits as detailed in the clinical monitoring plan and in accordance with DMID policies. Site monitoring is conducted to ensure that the human subject protections, study and laboratory procedures, study intervention administration, and data collection processes are of high quality and meet sponsor, ICH/GCP guidelines and applicable regulations; and that the study is conducted in accordance with the protocol, protocol-specific manual of procedures and applicable sponsor SOPs. Monitoring visits will include, but are not limited to, inspection of study facilities, review of regulatory files, accountability records, CRFs, informed consent forms (ICFs), printouts of medical and laboratory reports from the electronic medical records (EMR) system, and protocol and GCP compliance. Site monitors will have access to the study site, study personnel, and all study documentation according to the DMID-approved site monitoring plan. Study monitors will meet with SIs to discuss any problems and actions to be taken and document visit findings and discussions.

Site visits will be made at standard intervals as defined by DMID and may be made more frequently as directed by DMID. Following a monitoring visit the monitors will disseminate a report to the study site, the PI, CDM, CPM, and the PS.

11 STATISTICAL CONSIDERATIONS

11.1 Study Hypotheses

The primary objective of this study is to determine whether there is a significant difference in the urogenital chlamydia treatment failure rate in males treated with azithromycin 1 gm who do versus do not have urethral symptoms. We hypothesize that the chlamydia treatment failure rate will be significantly higher in males with urethral symptoms compared with no symptoms at the time of azithromycin treatment. The primary endpoint, treatment failure, will be evaluated at the Day 28 follow-up visit (Visit 2). As a secondary endpoint, treatment failure will be evaluated based on treatment outcome assessed at the Day 28 follow-up visit (Visit 2) and all non-study visits. Secondary objectives of the study are to determine whether the enrollment OmpA genotype and the enrollment *C. trachomatis* organism load are associated with treatment failure.

We hypothesize that OmpA genotype will not be associated with treatment failure, however there will be a significantly higher median *C. trachomatis* organism load in those with treatment failure compared to the median load in those without treatment failure.

11.2 Sample Size Considerations

The primary outcome measure is chlamydia treatment failure, and the primary endpoint is occurrence of treatment failure at the Day 28 follow-up visit (Visit 2, see Section 3.2.1). The sample size calculation is based on data extrapolated from the recent analysis of the NIAID sponsored trial since the study would be extended in the same clinical setting and with similar clinical procedures. Of the factors that may influence the azithromycin treatment rate, presence of urethral symptoms is the primary one of interest based on preliminary findings from the initial RCT and findings from the two recent NGU studies.^{17,18} Assumptions are that 20% of enrolled chlamydia-infected males will have urethral symptoms and azithromycin treatment failures will occur in 10% of symptomatic men vs. 2% of asymptomatic men. To detect a significant difference at the one-sided 0.05 significance level with power of 0.80 will require a sample size of 357 evaluable males, approximately 72 symptomatic and 285 asymptomatic males. Assuming 20% of males enrolled will be unevaluable for azithromycin treatment failure (either due to leaving the YCF before the Day 28 test-of-cure follow-up visit (Visit 2) or due to having a negative enrollment CT test), a total of 446 males will need to be enrolled. In accordance with ICH Statistical Guidelines, a one-sided significance level is used for testing.

11.3 Planned Interim Analyses (if applicable)

11.3.1 Safety Review

The DSMB will receive an annual safety report, prepared by the study statistician with input from the PI, with each scheduled DSMB meeting. Because AEs are expected to be uncommon and

mostly of mild severity, we have not identified any specific safety criteria for stopping the study due to adverse events. Indeed, possible minor side effect of treatment will be monitored as one of the study outcomes. However, the DSMB will be independent of study investigators and will be able to make recommendations based on the data it receives. In addition, the DSMB will receive immediate notification of any SAE that could be related to the study. The DSMB will decide whether to halt enrollment.

The null hypothesis is that the treatment failure rate at the Day 28 follow-up visit (Visit 2) is 10% for males with urethral symptoms (discharge and/or dysuria) versus 2% for males without urethral symptoms. After half of the study participants have Day 28 follow-up visit (Visit 2) outcome data available, an interim analysis will be performed.

The DSMB will receive an independent presentation of interim results, prepared by the study statistician. In preparation for each annual DSMB meeting, we will prepare summary reports of recruitment (by site), known outcome events, and any adverse events (including medication side effects). In addition, one interim analysis of the primary efficacy outcomes will occur when half of subjects have Day 28 follow-up visit (Visit 2) outcome data available using the Lan-DeMets spending function with an O'Brien-Fleming boundary for the values of the boundaries and the associated operating characteristics) to maintain the overall significance level of 0.05 for the primary outcome analysis, and to assess the significance of the interim results that emerge during the trial. The purpose of the interim analysis is to determine whether a difference in efficacy between symptomatic and asymptomatic participants can be established early before all participants are enrolled and complete follow-up.

Information Rate	Reject H_0 (one-sided)	P-value
0.50	$Z > 2.538$	0.006
1.00	$Z > 1.662$	0.05

11.4 Analysis Population

The primary analysis population for treatment failure will be the per protocol population, which is comprised of subjects who complete therapy and whose failure status can be established at the Day 28 follow-up visit (Visit 2). See Section 3.2.1 for definitions of evaluable subjects for the per protocol population.

11.5 Final Analysis Plan

For each of the two groups of males (those with versus without urethral symptoms), the binomial proportion and its 95% confidence interval will be used to estimate the failure rate. The Mantel-Haenszel-Cochran test will be used to compare the two groups across YCFs with respect to failure rate. To evaluate racial and ethnic group variation with respect to failure rate, a logistic

regression analysis will be performed with failure rate as the outcome variable, and with symptom status (symptomatic, asymptomatic), race and ethnicity included as covariates. While the primary analysis will use the combined urethral symptom variable (discharge and/or dysuria), secondary analyses with each urethral symptom will also be performed.

An ordinal scale will be used to quantify the intensity of each AE (0-None, 1-Mild, 2-Moderate, and 3-Severe). The incidence and severity level of AEs will be summarized for all subjects for each visit.

To assess the association between clinical/laboratory parameters and chlamydia treatment failure, including OmpA genotype and *C. trachomatis* organism load, univariate analyses of each factor against treatment failure will be conducted using Fisher's exact test for dichotomous factors and the Wilcoxon rank sum test for continuous variables. Those which are statistically significant at the 0.10 level will be incorporated into a logistic regression model. Since the underlying treatment failure rate is expected to be 0.04 (approximately 13 of 357 evaluable subjects), it may be difficult to identify characteristics that are associated with failure rate.

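### The version of the primary Mantel-Haenszel test is not stated for either look; if the uncorrected form is used and failure rates are 2-4%, overall one-sided error is about 0.062-0.071, not 0.05

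*Combined protocol and SAP*

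**What the plan says.** - **Final test (section 11.5).** "The Mantel-Haenszel-Cochran test will be used to compare the two groups across YCFs with respect to failure rate". No version of the test is given. Fisher's exact test is mentioned in the same section, but only for the secondary univariate analyses.
- **Interim look (section 11.3.1).** "one interim analysis of the primary efficacy outcomes will occur when half of subjects have Day 28 follow-up visit (Visit 2) outcome data available". A Lan-DeMets spending function of O'Brien-Fleming type is used "to maintain the overall significance level of 0.05 for the primary outcome analysis", with tabulated boundaries Z > 2.538 at half information and Z > 1.662 at full information. No test statistic is named.
- **Sizing (section 11.2).** "To detect a significant difference at the one-sided 0.05 significance level with power of 0.80 will require a sample size of 357 evaluable males", split into "approximately 72 symptomatic and 285 asymptomatic males". The planning values behind it read: "20% of enrolled chlamydia-infected males will have urethral symptoms and azithromycin treatment failures will occur in 10% of symptomatic men vs. 2% of asymptomatic men". No formula is named.
- **Expected events (section 11.5).** An underlying failure rate of 0.04, described as "approximately 13 of 357 evaluable subjects".

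**The concern.** The boundaries are normal-theory values, so they hold 0.05 only if the statistic is close to standard normal under the null. With roughly 7 to 14 failures in total (357 × 0.02 = 7.1; 357 × 0.04 = 14.3) and only a fifth of participants symptomatic, the uncorrected Mantel-Haenszel statistic is discrete and right-skewed. The planned test looks in the direction of the skew. At the interim, with about 178 participants, only 3.6 to 7.1 failures are expected.

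An ordinary reading of the named test could therefore miss the 0.05 that section 11.3.1 says is maintained, while a corrected version of the same test would keep it. The interim look is there to see whether a difference can be established early, so the version should be settled before those data exist.

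**Working it through.** **1. Boundaries.** O'Brien-Fleming-type spending at t = 0.5, one-sided 0.05: 2[1 − Φ(1.960/√0.5)] = 2[1 − Φ(2.772)] = 0.0056, so z = 2.538. Solving the second look from the bivariate normal with correlation √0.5 gives 1.662 and a total of 0.0500. The table reproduces. The nominal one-sided tail areas are 0.0056 and 0.048.

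**2. Sample size.** Inputs from section 11.2: p₁ = 0.10, p₂ = 0.02, ratio k = 4, one-sided 0.05, power 0.80.

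- Pooled rate: (0.10 + 4 × 0.02)/5 = 0.036.
- Uncorrected: n₁ = [1.645√(0.036 × 0.964 × 1.25) + 0.842√(0.09 + 0.0196/4)]² / 0.08² = 56.60, so N = 5 × 56.60 = 283.0.
- Continuity-corrected: n₁ = (56.60/4)[1 + √(1 + 2(1.25)/(56.60 × 0.08))]² = 71.37, so N = 356.8, which rounds to 357.
- Other one-sided routes: unpooled variance 458.4; arcsine 298.6; Fisher's exact test reaches 0.80 at about 355.

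**3. Two-look error with the stated boundaries.** Assumptions: the same statistic at both looks, an interim at 36/142 and a final at 72/285, and a common failure rate in both groups. Exact enumeration of the unstratified test, interim / overall one-sided error:

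| Common rate | Uncorrected | 0.5 correction | Conditional mid-p |
|---|---|---|---|
| 2% | 0.0166 / 0.0671 | 0.0033 / 0.0344 | 0.0033 / 0.0360 |
| 3% | 0.0139 / 0.0656 | 0.0040 / 0.0340 | 0.0040 / 0.0418 |
| 3.6% | 0.0125 / 0.0653 | 0.0042 / 0.0332 | 0.0042 / 0.0439 |
| 4% | 0.0118 / 0.0646 | 0.0042 / 0.0331 | 0.0043 / 0.0446 |
| 5% | 0.0109 / 0.0618 | 0.0042 / 0.0341 | 0.0044 / 0.0460 |
| 10% | 0.0091 / 0.0540 | 0.0043 / 0.0346 | 0.0050 / 0.0472 |

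**4. Stratification.** The documents list 15 YCFs but no enrolment per YCF, so layouts were assumed (1, 5 or 15 strata; equal and unequal sizes; fixed or random symptom counts). In simulations at 2-4%, uncorrected overall error was about 0.062-0.071. The 0.5-corrected test gave about 0.026-0.035 and mid-p about 0.036-0.045.

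**5. Power under 10% vs 2%, across layouts.**

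| Version | Overall power | Interim crossing |
|---|---|---|
| Uncorrected | 0.87-0.89 | 0.36-0.43 |
| 0.5 correction | about 0.80-0.83 | 0.21-0.29 |
| Mid-p | 0.84-0.85 | 0.23-0.29 |

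The corrected test dips just below 0.80 in some 15-YCF layouts (0.796 with unequal YCFs).

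**6. Tables on which the version decides.** Unstratified, with E = n₁m/N and V = n₁n₂m(N − m)/[N²(N − 1)], where m is the total number of failures.

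- Interim, 2/36 vs 0/142: E = 0.404, √V = 0.566. Uncorrected Z = 1.596/0.566 = 2.82, above 2.538. Corrected Z = 1.096/0.566 = 1.93, below it. The exact conditional one-sided probability is (36 × 35)/(178 × 177) = 0.040, so mid-p is 0.020, well above 0.0056.
- Final, 5/72 vs 7/285: E = 2.420, √V = 1.368. Uncorrected Z = 1.89; corrected Z = 1.52. They fall on opposite sides of 1.662.

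**The case against.** The strongest reply is that this is incomplete specification rather than an error. The plan names a recognised stratified test, its boundaries are right, and nothing says that the uncorrected form will be used. That stands: a reader might infer that the plan as written inflates type I error, and the documents do not support that. Inflation follows only under one of several readings of the named test. Nor do they suggest that anyone means to choose the version after seeing interim data; they only leave that possible.

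Second, the size rests on a null failure rate and YCF sizes that the plan does not give. That also stands. The 2-4% range is consistent with the failures expected in section 11.5, and the excess gets smaller at higher rates. The interim excess of about one percentage point is already inside the overall figure and is not a second harm.

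Third, it is tempting to conclude from N = 357 that a continuity-corrected test was intended. The match (356.8 against 283.0) is suggestive, but section 11.2 names no formula, Fisher's exact test fits about as well at 355, and the formula ignores both YCF strata and the interim look. The sizing is consistent with a correction and does not prove one.

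What does not fall away is that the version is unstated for both looks, and that an ordinary choice breaks the level the plan says it keeps.

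**Conclusion.** The concern holds as a gap in specification that should be closed. With 2.538 and 1.662, an uncorrected Mantel-Haenszel statistic has overall one-sided error of about 0.062-0.071 at common failure rates of 2-4%, an excess of 1.2 to 2.1 percentage points over 0.05. About 0.012-0.017 of the total is spent at the interim, against 0.0056 planned. At a 10% rate the overall figure is about 0.054. The 0.5-corrected and mid-p versions stayed below 0.05 in every layout checked.

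The result assumes the same test at both looks, a look at about 178 participants, and the failure rates and YCF layouts stated above. Confidence is high on the omission and the error rates, but not on which version was intended. The boundaries and the sample size are not at fault.

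**What to change.** In section 11.5, cross-referenced in section 11.3.1 and before any interim data are seen, name one small-sample version for both looks.

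- **Preferred:** a one-sided conditional mid-p test stratified by YCF, at nominal levels of about 0.0056 (interim) and 0.048 (final).
- **Acceptable alternative:** the one-sided Mantel-Haenszel test stratified by YCF with a 0.5 continuity correction, Z = (Σ(observed − expected symptomatic failures) − 0.5)/√Σ(hypergeometric variance), compared with 2.538 and 1.662.

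The same sentence should say which YCF defines a participant's stratum, since section 12 notes that minors may be transferred between facilities.

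Cost: one sentence and a cross-reference, with N = 357 and the boundaries unchanged. Compared with the uncorrected test (power 0.87-0.89), power falls to about 0.84-0.85 with mid-p or about 0.80-0.83 with the correction, the latter slightly under 0.80 in some layouts. The chance of crossing at the interim under 10% vs 2% falls from 0.36-0.43 to about 0.21-0.29. Mid-p needs exact stratified software; the corrected test does not, but it is conservative, with overall error of about 0.03.

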We hypothesize that the chlamydia treatment failure rate following azithromycin 1 gm administration will be significantly higher in males reporting urethral symptoms at the time of treatment. We also hypothesize that: 1) the enrollment OmpA genotype will not be associated with treatment failure, and 2) however a higher enrollment *C. trachomatis* organism load will be associated with a higher treatment failure rate.

Because study participant accrual rates at a single Los Angeles (LA) County YCF are too small to permit timely answers to the pressing question of frequency of chlamydia treatment failure in males following azithromycin administration, we propose to enroll at multiple YCFs in the LA County Correctional System, as was done for the prior clinical trial, to address our hypotheses. Facilities may be central detention centers, camps and/or placements that are part of the LA County YCF system.

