8.2.2 Special Assays or Procedures

C. trachomatis OmpA genotyping will be performed on urine specimens at UAB in [name] laboratory under his direct supervision by previously reported methodology.¹⁹ CT organism load quantification will also be performed on stored urine specimens at [name] [name]'s laboratory at UAB using real-time PCR (Cobas® 4800, Roche, Indianapolis, IN, USA). To estimate organism load, a *C. trachomatis* calibrator is run using stock *C. trachomatis* samples with known organism counts to create cycle threshold standard curves for comparison with clinical samples, providing reliable and reproducible results that allow for relative quantification on a log scale.

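### Secondary analyses, section 11.5: with about 13 failures, an ordinary race and ethnicity logistic fit can leave a group without a finite odds ratio, and effect estimates for clinical and laboratory factors come only after a p<0.10 screen that overstates modest dichotomous effects

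*Combined protocol and SAP*

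**What the plan says.** Section 11.5 plans two logistic models beyond the primary Mantel-Haenszel-Cochran comparison.

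- **Race and ethnicity model.** This is a logistic model: "regression analysis will be performed with failure rate as the outcome variable, and with symptom status (symptomatic, asymptomatic), race and ethnicity included as covariates". Its stated purpose is to evaluate racial and ethnic variation in failure. These three terms enter without any screen.
- **Predictor model.** Each clinical or laboratory factor, including OmpA genotype and organism load, is first tested against failure with Fisher's exact test if dichotomous, or "the Wilcoxon rank sum test for continuous variables". Then: "Those which are statistically significant at the 0.10 level will be incorporated into a logistic regression model".

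The section expects "approximately 13 of 357 evaluable subjects" to fail and cautions that "it may be difficult to identify characteristics that are associated with failure rate". It names no penalized or exact estimator and no rule for pooling small race or ethnicity levels. It names no effect estimate for a clinical or laboratory factor that does not pass the screen. The expected race and ethnicity mix is not given anywhere in the documents.

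**The concern.** Thirteen events are few for either model, and two separate problems arise.

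1. Under ordinary maximum likelihood, a level with no failures has a log-odds ratio that runs to minus infinity. If that level is the reference, every contrast with it is non-finite. A model meant to describe variation between groups would then have no usable estimate for one of them.
2. The univariate step names tests only. For clinical and laboratory factors, the only estimates planned are therefore those that survive p<0.10. With so few events, a modest factor passes mainly in trials where chance has made its estimate too large.

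At stake is the secondary objective on predictors of failure. A reader could be given a predictor at about twice its true odds ratio, or no estimate for a racial or ethnic group. The caution in 11.5 concerns predictors being missed and covers neither case.

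**Working it through.** **Inputs.** Section 11.2 gives 72 symptomatic and 285 asymptomatic evaluable men and assumes that "azithromycin treatment failures will occur in 10% of symptomatic men vs. 2% of asymptomatic men". Section 11.5 gives the two models and the 0.10 threshold. Race mix, factor shares, the number of candidate factors and all effect sizes other than that for symptoms are assumptions.

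**The plan's own figure.** Expected failures are 72 × 0.10 = 7.2 among symptomatic men and 285 × 0.02 = 5.7 among asymptomatic men, in total 12.9, which is 3.6% of 357. This agrees with the stated 13 and 0.04. The central 95% range of the count is 7 to 20. The odds of failure are 0.10/0.90 = 0.111 with symptoms and 0.02/0.98 = 0.0204 without, so the symptom odds ratio is 5.44.

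**Part 1: empty levels.** Take a group of m men with 20% symptomatic and no race effect. Then P(no failures) = 0.90^(0.2m) × 0.98^(0.8m).

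| Group size m, share of 357 | P(no failures) |
|---|---|
| 18 men, 5% | 0.51 |
| 36 men, 10% | 0.26 |
| 71 men, 20% | 0.07 |
| 107 men, 30% | 0.02 |
| 179 men, 50% | 0.001 |

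The chance of at least one empty race level was simulated with failures drawn as Binomial(72, 0.10) plus Binomial(285, 0.02) and allocated at random to levels:

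| Assumed race mix (%) | At least one empty level |
|---|---|
| 50/50 | 0.3% |
| 70/30 | 2% |
| 40/40/20 | 8% |
| 50/40/10 | 28% |
| 50/30/15/5 | 60% |

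The full symptom + race + ethnicity model (ethnicity assumed 60/40) had all coefficients finite under the ordinary fit in 99%, 70% and 39% of trials for 50/50, 50/40/10 and 50/30/15/5. Under Firth it was 100%. Coverage of the Firth 95% profile interval was 0.954 to 0.974 for the smallest race level and 0.953 to 0.955 for symptoms.

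Example: 0 of 36 against 13 of 321. The ordinary odds ratio is 0, with no finite logarithm. In a 2×2 table Firth amounts to adding 0.5 to each cell: odds of 0.5/36.5 = 0.0137 against odds of 13.5/308.5 = 0.0438, a ratio of 0.31, with profile 95% interval 0.002 to 2.4. The likelihood-ratio test still gives an answer, p = 0.09.

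**Part 2: the screen.** To see the mechanism, take a factor present in 107 of 357 men (30%) and 13 failures in total. Failures of 6/107 against 7/250 give an odds ratio of 6 × 243 divided by 7 × 101, which is 2.06, and Fisher p = 0.22, so the factor is dropped. Moving one failure, 7/107 against 6/250 gives 7 × 244 divided by 6 × 100, which is 2.85, and p = 0.07, so it is kept. A table that estimates a true odds ratio of 2 almost exactly does not pass.

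Exact enumeration of all tables (N = 357, overall failure rate 12.9/357, factor share 20% to 50%, two-sided Fisher p<0.10) gives:

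| True OR | Pass the screen | Median OR, all trials | Median OR, kept |
|---|---|---|---|
| 2 | 29% to 32% | 2.0 to 2.1 | 3.7 to 4.2 |
| 3 | 54% to 59% | 3.0 to 3.1 | 4.2 to 4.7 |
| 5.44 | 81% to 88% | 5.3 to 5.8 | 6.1 to 7.3 |

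Relative to the truth, the kept median is 3.7/2 to 4.2/2 = 1.8 to 2.1 times at a true OR of 2, and 4.2/3 to 4.7/3 = 1.4 to 1.6 times at 3.

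The multivariable model behaves the same way. With eight assumed candidates (symptoms, load and six dichotomous factors), a true OR of 2 was kept in 27% to 28% of trials with median 3.9, and a true OR of 3 in 54% with median 4.4. At least one null factor was kept in 24% to 30% of trials. A coefficient was non-finite in 3.5% to 5.8% of fitted models.

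Organism load was screened by Wilcoxon p<0.10, with log load taken as normal:

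| True OR per SD | Pass | Median OR, kept |
|---|---|---|
| 1.25 | 20% | 1.82 |
| 1.5 | 41% | 1.94 |
| 2 | 74% | 2.22 |
| 3 | 96% | 3.07 |

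**The case against.** Several points on the other side are sound.

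- A reader might infer that every predictor odds ratio in 11.5 is screened. That is not so. Symptom status, race and ethnicity enter their own model unscreened, and part 2 applies only to the clinical and laboratory factors.
- A reader might infer that the question of racial and ethnic variation cannot be answered. The likelihood-ratio test works with an empty level, so only the estimate fails. Section 11.5 also names no fitting method, so part 1 is conditional on an ordinary fit.
- The stated secondary hypotheses do not rest on the screened odds ratios. Section 2.2 expects that a higher "organism load will be associated with a higher treatment failure rate", and section 11.1 puts this as a difference in medians, which the unscreened Wilcoxon test addresses directly. For load, inflation matters only at small effects.
- The documents posit no dichotomous factor with an odds ratio of 2 or 3; these are illustrative values. The race mix is likewise unknown, and the risk spans negligible to likely.
- The plan already tells readers that these analyses are weak.

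These limit the point but do not remove it. Choosing how to pool or penalize after seeing which level is empty would be a data-driven choice. The plan's caution is about low power; it does not warn that a factor which is found may be reported too large.

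**Conclusion.** The point holds as a minor one, for secondary analyses only. With about 13 failures, an ordinary fit of the race and ethnicity model leaves at least one race level without a finite odds ratio in about 0.3% to 60% of trials. This is likely to matter only if some level holds roughly 10% of the men or fewer. For clinical and laboratory factors, the screen roughly doubles a true dichotomous odds ratio of 2 when the factor is kept, and the inflation shrinks as the true effect grows. It is slight for organism load from about 2 per SD upward. The expected failure count follows from the plan's own inputs; race mix, factor shares, candidate set and effect sizes other than symptoms are assumed.

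A reader might infer that the symptomatic versus asymptomatic comparison is compromised. The documents do not support that: the primary analysis is a separate Mantel-Haenszel-Cochran test and uses neither model.

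**What to change.** Amend section 11.5 as follows.

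(a) Fit the symptom + race + ethnicity model by Firth-penalized logistic regression with profile-likelihood intervals. Use the same estimator for the screened model in every case, not only when an empty cell appears, so that the choice does not depend on the data. Pre-stated pooling of small levels is an alternative, but a pooled group then has no estimate of its own.

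(b) Report an unscreened univariate odds ratio with profile interval, by the same Firth estimator, for every clinical and laboratory factor tested, whether or not it passes p<0.10. Include each OmpA genotype level, and organism load per log unit, since section 8.2.2 says the assay results "allow for relative quantification on a log scale". Label the screened-model estimates exploratory.

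The estimator must be named in (b). With ordinary fits and no effect, a dichotomous factor with a 10% share would have no finite odds ratio in about 27% of trials, and an assumed five-level genotype split of 35/25/20/10/10 would have an empty level in about 54%.

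The Fisher and Wilcoxon tests and the screen may stay. The cost is SAP wording, one software option and one extra table. The downsides are visibly wide intervals for weak factors and slight shrinkage: at a true symptom odds ratio of 5.44, the median is 5.2–5.4 under Firth against 5.4–5.7 under the ordinary fit. Firth does not remove the screen inflation (median 3.6–3.8 at a true odds ratio of 2 in the screened model); the unscreened table makes it visible.
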